4.4. ACUIITY X4 Quadripolar Coronary Venous Lead and Associated Accessory Models

Table 1 includes the model numbers and lead lengths of the ACUIITY X4 leads.

Table 1: ACUIITY X4 Lead Models

Tip Configuration	Electrode Spacing	Length	
		86cm	95cm
		Model Number	
Straight	Even	4671	4672
Spiral	Short tip	4674	4675
	Long tip	4677	4678

Table 2 includes the accessories used with ACUIITY X4 leads.

Table 2: ACUIITY X4 Lead Accessories

Component	Model Number**
ACUIITY X4 Flushing Tool*	4604
ACUIITY X4 Connector Tool*	4625
Vein Pick*	6541
Quadripolar Connector Lead Cap	7007
Slit Suture Sleeve (optional)	4603

*These accessories packaged with ACUIITY X4 leads (model numbers do not apply)

**Model numbers to order components as accessories

4.5. RELIANCE 4-FRONT Ventricular Defibrillation Leads

The RELIANCE 4-FRONT lead is designed for right-side heart applications within the ventricle, atrium, and superior vena cava. It is equipped with one quadripolar connector defined by ISO 27186 [Active Implantable medical devices – Four-pole connector system for implantable cardiac rhythm management devices], which contains both high and low voltage connections. RELIANCE 4-FRONT is intended for permanent sensing, pacing, and defibrillation when used with a compatible Implantable Cardioverter Defibrillator (ICD) (not for the NAVIGATE X4 Study) or Cardiac Resynchronization Therapy Defibrillator (CRT-D). For the purpose of the

NAVIGATE X4 Clinical Study, only commercially available or investigational BSC CRT-Ds with quad headers are allowed. The RELIANCE 4-FRONT lead is designed to be placed into the venous anatomy through an 8 Fr introducer.

Refer to Section 25.2 for a more detailed description of this lead.

4.6. RELIANCE 4-FRONT Lead and Associated Accessory Models

Table 3 contains the model numbers and lead lengths of the RELIANCE 4-FRONT Leads.

Table 3: RELIANCE 4-FRONT Lead Models

		Lead Length		
		59cm	64cm	70cm
Lead Fixation Type	Lead Type	Model Number		
Active	Dual Coil	0675	0676	NA
	Single Coil G	0692	0693	0657
	Dual Coil G	0695	0696	0658
Passive	Dual Coil	0665	0636	NA
	Single Coil G	0682	0683	0654
	Dual Coil G	0685	0686	0655

G= Gore ePTFE (expanded-polytetrafluoroethylene) covered coil(s)

Table 4 includes the accessories used with RELIANCE 4-FRONT Leads.

Table 4: RELIANCE 4-FRONT Accessories

Component	Accessory Model Number
Soft Straight Stylets	6601 (59cm), 6964 (70cm), 6972 (64cm)
Firm Straight Stylets	6602 (59cm), 6963 (70 cm), 6971 (64cm)
Vein Pick	6541
Quadripolar Connector Lead Cap	7007
EZ-4 Connector Tool	7001
Tunneler Accessory Kit	6888
Quadripolar Lead Pulling Tip	7006
Slit Suture Sleeve (optional)	6403

4.7. Boston Scientific X4 CRT-Ds

Boston Scientific’s new family of CRT-D devices include several models as listed in Table 5. They provide a variety of therapies including:

- Ventricular tachyarrhythmia therapy used to treat rhythms associated with sudden cardiac death such as VT and VF,

- CRT which treats heart failure by resynchronizing ventricular contractions through biventricular electrical stimulation, and
- Bradycardia pacing, including adaptive rate pacing, to detect and treat bradyarrhythmias and to provide cardiac rate support after defibrillation therapy.

This family of CRT-Ds includes models that are not intended to accept quadripolar coronary venous LV leads (they accept IS-1 or LV-1 coronary venous leads). Those models in the family that are compatible with quadripolar coronary venous leads include “X4” in their name and are listed in Table 5 below. As a family of devices, they will be referred to as BSC X4 CRT-Ds. All models in the BSC X4 CRT-D family may be implanted in NAVIGATE X4 once commercially available. The AUTOGEN X4 CRT-D devices are investigational in the US until approval of AUTOGEN (non X4) CRT-D devices; they may be used in NAVIGATE X4 while investigational. Therefore, there is one algorithm included in the AUTOGEN X4 that is investigational in the US until approval of AUTOGEN; it is PaceSafe, which is described further in Section 4.7.1.

Table 5: Boston Scientific X4 CRT-Ds Allowed in NAVIGATE X4

Device Name	US Model Numbers	International Model Numbers	Description of Port RV/ LV/ RA
AUTOGEN™ X4	G166*	G177	DF1/ IS4/ IS1
AUTOGEN™ X4	G168*	G179	DF4/ IS4/ IS1
DYNAGEN™ X4	G156	G156	DF1/ IS4/ IS1
DYNAGEN™ X4	G158	G158	DF4/ IS4/ IS1
INOGEN™ X4	G146	G146	DF1/ IS4/ IS1
INOGEN™ X4	G148	G148	DF4/ IS4/ IS1
ORIGEN™ X4	G056	G056	DF1/ IS4/ IS1
ORIGEN™ X4	G058	G058	DF4/ IS4/ IS1

*AUTOGEN X4 will be investigational in the US during a portion of the study

4.7.1. PaceSafe Feature Overview

The PaceSafe feature consists of two independent automatic pacing threshold determination algorithms: Right Atrial AutoThreshold (RAAT), and Right Ventricular AutoThreshold (RVAT) in AUTOGEN X4. The PaceSafe feature is designed to dynamically adjust the pacing output, independently in each chamber, to ensure capture by optimizing the output voltage to an adequate safety margin.

The PaceSafe algorithm will be studied in a separate clinical study.

Please refer to the AUTOGEN X4 Physician’s Technical Guide for more information regarding PaceSafe.

Note: Although PaceSafe will be investigational in the US during a portion of the NAVIGATE X4 Study, investigators may program the feature ON at their discretion. Programming of these features will be collected for NAVIGATE X4.

4.7.1. RightRate Feature Overview

The international AUTOGEN X4 models (G177, G179) will also include the RightRate feature that uses the minute ventilation sensor as a rate driver for subjects with chronotropic incompetence. The RightRate feature is not available in AUTOGEN X4 models in the US (G166, G168).

Please refer to the AUTOGEN X4 Reference Guide for additional information on the RightRate feature.

5. OBJECTIVES

The objective of the NAVIGATE X4 Clinical Study is to gather data to establish the safety, performance and effectiveness of the ACUITY X4 quadripolar coronary venous leads and the RELIANCE 4-FRONT ventricular defibrillation leads to satisfy FDA requirements for pre-market submission. Additionally, data from this study will be used to support post-market approval requirements for the ACUITY X4 and RELIANCE 4-FRONT leads.

6. ENDPOINTS

6.1. ACUITY X4 Endpoints

The following endpoints will be evaluated to establish safety, performance, and effectiveness of the ACUITY X4 leads to satisfy US regulatory requirements.

6.1.1. Safety Endpoints

- Primary Safety Endpoint: Lead-related CFR from Implant through 6 Months Post-Implant.
- Ancillary Safety Objective: Chronic Lead-related CFR through 60 Months Post-Implant (Data from the NAVIGATE X4 Clinical Study will be pooled with data from a separate Post-Market Approval Study for analysis of this objective)

6.1.2. Effectiveness Endpoints

- Primary Effectiveness Endpoint 1: LV Lead Pacing Capture Thresholds in the programmed configuration at 3 months post-implant for ACUITY X4 [REDACTED] Responders are defined as subjects with PCT \leq 2.5 V in the programmed configuration
- Primary Effectiveness Endpoint 2: LV Lead Pacing Capture Thresholds in the proximal zone (E2, E3, or E4) at 3 months post-implant for ACUITY X4 [REDACTED]
- Secondary Effectiveness Endpoint 1: Sensed Amplitude in the programmed configuration at Three Months Post-Implant
- Secondary Effectiveness Endpoint 2: Pacing Impedance in the programmed configuration at Three Months Post-Implant

December 17, 2013
FINAL

Boston Scientific
NAVIGATE X4 Study Protocol
90874504 Version AB
Page 25 of 101

6.2. RELIANCE 4-FRONT Endpoints

The following endpoints will be evaluated to establish safety, performance, and effectiveness of the RELIANCE 4-FRONT leads, to satisfy US regulatory requirements.

6.2.1. Safety Endpoints

- Primary Safety Endpoint 1: Lead-related CFR from Implant through 3 Months Post-Implant
- Primary Safety Endpoint 2: Lead-related CFR from 3 through 24 Months Post-Implant
- Secondary Safety Endpoint: Detection of VT/VF within 30 days of implant
- Ancillary Safety Objective: Chronic Lead-related CFR through 60 Months Post-Implant (Data from the NAVIGATE X4 Clinical Study will be pooled with data from a separate Post-Market Approval Study for analysis of this objective)

6.2.2. Effectiveness Endpoints

- Primary Effectiveness Endpoint: RV Lead Pacing Capture Threshold at 0.5 ms pulse width at Three Months Post-Implant
- Secondary Effectiveness Endpoint 1: Sensed Amplitude at Three Months Post-Implant
- Secondary Effectiveness Endpoint 2: Pacing Impedance at Three Months Post-Implant
- Secondary Effectiveness Endpoint 3: VT/ VF Shock Conversion, analyzed within 30 days of implant

7. DESIGN

The NAVIGATE X4 Clinical Study is a prospective, single-arm, non-randomized, multi-center, global clinical study, utilizing performance goals, to demonstrate the safety, performance and effectiveness of the ACUITY X4 LV and RELIANCE 4-FRONT RV Leads. [REDACTED]

7.1. Scale and Duration

[figure not shown]
The NAVIGATE X4 Clinical Study will [REDACTED] to enroll between 1542 and 2290 subjects at up to 125 centers in the United States, Israel, and Canada. [REDACTED]

[REDACTED] ACUITY X4 leads are required to be implanted or attempted, whereas RELIANCE 4-FRONT is [REDACTED]

December 17, 2013
FINAL

Boston Scientific
NAVIGATE X4 Study Protocol
90874504 Version AB
Page 26 of 101

F

[Redacted text block]

[Redacted text block]

[Redacted text block]

December 17, 2013
FINAL

Boston Scientific
NAVIGATE X4 Study Protocol
90874504 Version AB
Page 27 of 101

Subjects will be consented and followed for 5 years following implant to fulfill worldwide regulatory post-market approval requirements. See Figure 3.

[figure not shown]

Figure 3: NAVIGATE X4 Clinical Study Design

7.2. Justification for the Study Design

To appropriately characterize performance of new lead families, the United States Food and Drug Administration (FDA) requires that the various leads in a lead family be studied [redacted] with minimum sample sizes for each [redacted] depending on the type of lead.

[Redacted text block]

[redacted]	[redacted]	[redacted]	[redacted]	[redacted]
[redacted]	[redacted]	[redacted]	[redacted]	[redacted]
[redacted]	[redacted]	[redacted]	[redacted]	[redacted]
[redacted]	[redacted]	[redacted]	[redacted]	[redacted]
[redacted]	[redacted]	[redacted]	[redacted]	[redacted]

[Redacted text block]

December 17, 2013
FINAL

Boston Scientific
NAVIGATE X4 Study Protocol
90874504 Version AB
Page 28 of 101

8. SUBJECT SELECTION

8.1. Study Population and Eligibility

Subjects included in the NAVIGATE X4 Clinical Study should be selected from the investigator's general patient population indicated for CRT-D implantation. Investigators are responsible for screening all potential subjects and selecting those who meet the eligibility criteria for the study as described in Sections 8.2 and 8.3 below.

8.2. Inclusion Criteria

Subjects who meet all of the following criteria may be given consideration for inclusion in this clinical study, provided no exclusion criterion (see Section 8.3) is met.

- Subjects indicated for a CRT-D that fulfill one of the following 5 criteria^[1]:
 1. Subject with LVEF less than or equal to 35%, sinus rhythm, LBBB with a QRS duration greater than or equal to 150 ms, and a NYHA class II, III or ambulatory IV symptoms on GDMT*
 2. Subject with LVEF less than or equal to 35%, sinus rhythm, LBBB with a QRS duration 120 to 149 ms, and NYHA class II, III, or ambulatory IV symptoms on GDMT*
 3. Subject with LVEF less than or equal to 35%, sinus rhythm, a non-LBBB pattern with a QRS duration greater than or equal to 150 ms, and NYHA class III/ ambulatory class IV symptoms on GDMT*
 4. Subject with atrial fibrillation and LVEF less than or equal to 35% on GDMT* if a) the subject requires ventricular pacing or otherwise meets CRT criteria [listed here] and b) AV nodal ablation or pharmacologic rate control will allow near 100% ventricular pacing with CRT
 5. Subject on GDMT* who have LVEF less than or equal to 35% and are undergoing new device placement with anticipated requirement for significant (>40%) ventricular pacing

*GDMT = Guideline-directed medical therapy (formerly known as optimal pharmaceutical therapy (OPT)), represents optimal medical therapy as defined by ACCF/ AHA guideline-recommended therapies (primarily Class I)

- Subject is intended to receive the ACUITY X4 LV lead and RELIANCE 4-FRONT RV lead (optional in Study Phase 1) and BSC CRT-D with quad header as their initial (*de novo*) cardiac implants
- Subject is willing and capable of providing informed consent (which can include the use of a legally authorized representative (LAR) for documentation of informed consent) and participating in all testing associated with this investigation at an approved center and at the intervals defined by this protocol

December 17, 2013
FINAL

Boston Scientific
NAVIGATE X4 Study Protocol
90874504 Version AB
Page 29 of 101

- Subject is age 18 or above, or of legal age to give informed consent specific to state and national law

8.3. *Exclusion Criteria*

Subjects who meet any one of the following criteria will be excluded from this clinical study.

- Subject has a known or suspected sensitivity to dexamethasone acetate (DXA)
- Subject has a mechanical tricuspid heart valve
- Subject is enrolled in any other concurrent study, with the exception of local mandatory governmental registries and observational studies/registries* that are not in conflict and do not affect the following:
 - Schedule of procedures for the Study (i.e. should not cause additional or missed visits);
 - Study outcome (i.e. involve medications that could affect the heart rate of the subject);
 - Conduct of the Study per GCP/ ISO 14155:2011/ 21 CFR 812, local regulations
- Subject is currently on the active heart transplant list
- Subject has a documented life expectancy of less than twelve months
- Women of childbearing potential who are or might be pregnant at the time of study enrollment or CRT-D System implant (method of assessment upon physician's discretion)
- Subjects currently requiring chronic dialysis

*Sponsors of such studies/registries should be informed and Boston Scientific must be informed by the investigator about the parallel conduct of these projects in the subject and of the project's basic nature. The decision if a desired mandatory governmental registry or observational study/ registry is in conflict with this exclusion criterion is up to the enrolling investigator.

9. SUBJECT ACCOUNTABILITY

9.1. *Point of Enrollment*

Subjects will be considered enrolled into the NAVIGATE X4 Clinical Study at the time of informed consent form execution. All subject enrollments will be counted against the enrollment ceiling for the study.

9.2. *Withdrawal*

All subjects enrolled in the clinical study (including those withdrawn from the clinical study or lost to follow-up) shall be accounted for and documented. If a subject withdraws from the clinical investigation, the reason(s) shall be reported. If such withdrawal is due to problems

December 17, 2013
FINAL

Boston Scientific
NAVIGATE X4 Study Protocol
90874504 Version AB
Page 30 of 101

related to investigational device safety or performance, the investigator shall ask for the subject's permission to follow his/her status/condition outside of the clinical study.

Reasons for withdrawal may include physician discretion, subject choice to retire consent, loss to follow-up, or death. While study withdrawal is discouraged, subjects may withdraw from the study at any time, with or without reason, and without prejudice to further treatment. All applicable electronic case report form (eCRFs) up to the point of subject withdrawal and an "End of Study" eCRF must be completed. For subjects who are "lost-to-follow-up" the investigator/center should have at least three documented attempts to contact the subject prior to completion of the "End of Study" eCRF. Additional data may no longer be collected after the point at which a subject has been withdrawn from the study or withdraws his/her consent, for whatever reason. All open adverse events should be closed or documented as chronic. Data collected up to the point of subject withdrawal may be used.

9.3. *Subject Status and Classification*

All patients who sign the Informed Consent form are considered enrolled in the study and count towards the enrollment ceiling. Subjects will be classified in the study database as follows:

Intent - refers to a subject who has been enrolled, but then does not undergo an implant procedure. The original Informed Consent form and screening documentation for intent patients should be maintained in the Center's files. There are no follow-up requirements for intent subjects; intent subjects must be withdrawn from the study.

Partial Attempt – refers to a subject who has been enrolled and has had anesthesia administered in preparation for the surgical implant procedure, but does not have an ACUITY X4 or RELIANCE 4-FRONT lead introduced into their vasculature. There are no follow-up requirements for partial attempt subjects; partial attempt subjects must be withdrawn from the study.

Note: In this case since neither study lead was implanted, US subjects may not be implanted with an AUTOGEN X4 CRT-D (while it is investigational)

Attempt - refers to a subject who 1) has been enrolled in the NAVIGATE X4 Study, 2) has had anesthesia administered in preparation for the surgical implant procedure, 3) has had either the ACUITY X4 or RELIANCE 4-FRONT lead introduced into the subject's vasculature, but 4) is not successfully implanted with either the ACUITY X4 lead or RELIANCE 4-FRONT lead.

Note: In this case since neither the RELIANCE 4-FRONT lead nor the ACUITY X4 lead was implanted, US subjects may not be implanted with an AUTOGEN X4 CRT-D (while it is investigational)

Attempt subjects must be followed 30 ± 7 days post-attempted ACUITY X4 and/or RELIANCE 4-FRONT lead implant to assure there are no associated adverse events, or to assure the resolution of any adverse events associated with the attempted ACUITY X4 and/or RELIANCE 4-FRONT lead implants. These subjects must be withdrawn from the study after satisfying the 30 ± 7 day follow up.

Implant - refers to a subject who is successfully implanted and/or tested with the ACUITY X4 and/or RELIANCE 4-FRONT Lead(s) per the study protocol. These subjects are

December 17, 2013
FINAL

Boston Scientific
NAVIGATE X4 Study Protocol
90874504 Version AB
Page 31 of 101

followed in accordance with the follow-up schedule included in this protocol and included in all analyses of safety, effectiveness, and performance.

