11. STATISTICAL CONSIDERATIONS

11.1. ACUITY X4 Endpoints

11.1.1. ACUITY X4 Primary Safety Endpoints

Safety of the ACUITY X4 lead will be evaluated by the lead-related complication-free rate (CFR) over a six-month follow-up period. [REDACTED]. Lead-related complications are lead-related adverse events resulting in permanent loss of pacing therapy, invasive intervention, injury or death. Lead-related adverse events are further defined in Section 19.3. Lead-related complications associated with attempted ACUITY X4 Lead implants will count toward this safety endpoint.

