11.1.3. Statistical Methods

To assess safety of the ACUITY X4 leads, the Kaplan-Meier six month (180-day) complication-free rate will be calculated. [redacted]
The analysis will be conducted when the last 6-month follow-up is completed [redacted]
[redacted] Data from all implanted or attempted [redacted] [redacted] leads will be included in the endpoint analysis.

December 17, 2013
FINAL

Boston Scientific
NAVIGATE X4 Study Protocol
90874504 Version AB
Page 49 of 101

[REDACTED]

The exact follow-up time for each ACUITY X4 lead in the 180-day post-implant period will be included in the analysis via Kaplan-Meier methodology. The leads that fail to reach 180 days of follow-up (without experiencing an endpoint event prior to their end of follow-up in the period) will be censored at the time of their end of follow-up in the period. Because non-informative censoring cannot be assumed for these leads, a tipping point analysis will be performed to determine the potential effects these censored leads could have on the results if full information on each lead was present. The tipping point analysis will assign each lead that was censored prior to 180 days as either having or not having an endpoint event. The tipping point will be determined by the point at which the endpoint results turn from passing (null hypothesis) to failing (null hypothesis rejected). An exact binomial test will be performed for the tipping point analysis.

11.1.4. ACUITY X4 Primary Effectiveness Endpoint 1

The first effectiveness endpoint for ACUITY X4 is pacing capture thresholds (PCT) in the programmed configuration. This endpoint will be evaluated at 3 months post-implant. [REDACTED] For this endpoint, responders will be defined as subjects with $PCT \leq 2.5$ V in the programmed configuration.

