11.2.1.3. Statistical Methods

Data from all subjects implanted or attempted with a RELIANCE 4-FRONT lead will be eligible for inclusion in the endpoint analysis. All RELIANCE 4-FRONT leads [REDACTED] will be pooled for this analysis.

The lead-related complication-free rate from date of implant (or date of attempt, for leads attempted but not implanted) through 91 days post-implant will be calculated using Kaplan-Meier methodology. The 95% one-sided lower pointwise confidence limit of the complication-free rate will be calculated via log-log methodology for all eligible subjects contributing to the analyses and compared to the performance goal of 93%. If the lower confidence limit exceeds 93%, the null hypothesis will be rejected.

Each lead's exact follow-up time in the 91 days post-implant will be included in the analysis via Kaplan-Meier methodology. The leads that fail to reach 91 days of follow-up (without

December 17, 2013
FINAL

Boston Scientific
NAVIGATE X4 Study Protocol
90874504 Version AB
Page 55 of 101

experiencing an endpoint event prior to their end of follow-up in the period) will be censored at the time of their end of follow-up in the period. Because non-informative censoring cannot be assumed for these leads, a tipping point analysis will be performed to determine the potential effects these censored leads could have on the results if full information on each lead was present. The tipping point analysis will assign each lead that was censored prior to 91 days as either having or not having an endpoint event. The tipping point will be determined by the point at which the endpoint results turn from passing (null hypothesis) to failing (null hypothesis rejected). An exact binomial test will be performed for the tipping point analysis.

11.2.2. RELIANCE 4-FRONT Primary Safety Endpoint 2

To satisfy the safety assessment requirements of the US Food and Drug Administration (FDA), safety of the RELIANCE 4-FRONT Leads will also be evaluated by the lead-related CFR from three months post-implant through 24 months post implant based on complications that are related to the RELIANCE 4-FRONT Lead during that period. The same definition of lead-related complication will be used for both RELIANCE 4-FRONT Primary Safety Endpoint 1 and Primary Safety Endpoint 2.

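### A complication that follows withdrawal over a lead problem cannot enter the primary safety endpoints, so the complication-free rates can be biased upward if such leavers carry above-average risk

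*Protocol*

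**What the plan says.** Protocol 9.2 requires the reason for every withdrawal to be reported. Where the reason is a device safety or performance problem, the investigator asks for "permission to follow his/her status/condition outside of the clinical study". The same section says: "Additional data may no longer be collected after the point at which a subject has been withdrawn from the study". That bar applies whatever the reason for leaving. Information from before withdrawal is kept: "Data collected up to the point of subject withdrawal may be used".

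Section 11.1.1 defines the ACUITY X4 endpoint event: "Lead-related complications are lead-related adverse events resulting in permanent loss of pacing therapy, invasive intervention, injury or death". Section 19.3.1 adds lead-related events that need intravenous drug therapy. Section 11.1.3 then takes the leads that fall short of 180 days "without experiencing an endpoint event prior to their end of follow-up in the period" and says that they "will be censored at the time of their end of follow-up in the period". Sections 11.2.1.3 and 11.2.3 apply the same rule to the two RELIANCE 4-FRONT primary safety endpoints. None of the three sections uses the withdrawal reason.

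All three sections acknowledge informative censoring. Section 11.1.3 puts it this way: "Because non-informative censoring cannot be assumed for these leads, a tipping point analysis will be performed to determine the potential effects". Each censored lead is assigned an event or no event, and an exact binomial test is run.

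**The concern.** A lead-related adverse event is not automatically an endpoint event. Section 19.3 lists failure to capture, abnormal impedance and extracardiac stimulation, among others. Under 19.3.1 these count only once they lead to permanent loss of pacing, invasive intervention, injury, death or intravenous drug treatment. A subject can therefore leave because of a lead problem that is still open and not yet a complication. If the lead is revised a month later, still inside the endpoint window, that revision is the event the endpoint exists to capture. Section 9.2 nevertheless places it outside the study and gives it no route back in.

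These subjects left because something was wrong with the lead, so above-average risk is plausible, although the documents do not show it. The comparison is single-arm against fixed goals, so no control group would share the bias. Sections 11.2.1.3 and 11.2.3 base the RELIANCE decision on the unadjusted Kaplan-Meier confidence limit. Under 11.3.1, success for each lead requires every primary endpoint to pass.

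**Working it through.** **Plan's own figure.** The synopsis states at least 80% power for all endpoints. The expected rates and attrition behind it are redacted, so it cannot be reproduced. Solving the normal approximation for the expected rate that would give 80% shows how much room there is:

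- N = 534 against 87%: 90.9% at one-sided 2.5%, or 90.5% at 5%.
- N = 1876 against 93%: 94.4% at 5%.
- N = 1876 against 94%: 95.3% at 5%.

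With full data, the exact test passes with at most 54 events (2.5%) or 56 events (5%) of 534, 112 of 1876 (93% goal) and 95 of 1876 (94% goal). That is about 5 to 7 events above the number expected at those rates. For example, 112 − 1876 × 0.056 ≈ 7.

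**Inputs from the documents.** The goals are 87% and 85% (11.1.1.1), 93% (11.2.1.1) and 94% (11.2.2.1). The ACUITY cohorts are 534 spiral and 214 straight leads (SAP 2.1). The RELIANCE dataset is 1876 leads (SAP 2.2). RELIANCE primary safety uses a one-sided 95% log-log limit.

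**Assumptions.**

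- 87% belongs to the 534-lead cohort and 85% to the 214-lead cohort.
- The ACUITY primary safety alpha is redacted, so 2.5% and 5% are both tried for the 534-lead cohort and 5% for the 214-lead cohort.
- Leavers exit early in the window.
- All 1876 RELIANCE leads follow the same withdrawal rule, although some come from other studies. For Primary Safety Endpoint 2, 1876 is an upper bound, because leads lost before its start day are excluded.

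**Bias.** Let T be the true complication-free rate, S the rate Kaplan-Meier targets, w the share leaving event-free over a lead problem, and q their later complication risk inside the window.

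T = (1 − w)S + w(1 − q), so S = [T − w(1 − q)] / (1 − w), and bias = S − T = w[q − (1 − S)].

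The bias is zero when leavers have average risk, negative when their risk is below average, and never more than w. At T = 87%, w = 1%:

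- q = 50%: 0.865 / 0.99 = 0.8737, bias 0.37 points.
- q = 100%: 0.870 / 0.99 = 0.8788, bias 0.88 points.

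| True rate = goal | w = 1%, q = 50% | w = 1%, q = 100% |
|---|---|---|
| 87% | 0.37 | 0.88 |
| 85% | 0.35 | 0.86 |
| 93% | 0.43 | 0.94 |
| 94% | 0.44 | 0.95 |

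At q = 100%, the range over w is 0.44 points (w = 0.5%) to 1.78 points (w = 2%) at the 87% goal, and 0.47 to 1.90 points at the 93% goal.

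**Chance of passing when the true rate equals the goal.** These are simulated with Kaplan-Meier and log-log lower limits, 4000 runs, 5% other censoring.

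| Case | No such leavers | w = 1%, q = 50% | w = 1%, q = 100% |
|---|---|---|---|
| N = 534, 87%, alpha 2.5% | 1.8% | 4.1% | 7.8% |
| N = 534, 87%, alpha 5% | 4.2% | 8.0% | 14.2% |
| N = 214, 85%, alpha 5% | 4.4% | 6.1% | 8.6% |
| N = 1876, 93%, alpha 5% | 4.2% | 18.8% | 49.3% |
| N = 1876, 94%, alpha 5% | 4.7% | 21.2% | 55.9% |

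**Tipping point.** Counting every censored lead as an event passes in 0.1% of runs or fewer in every scenario. This holds equally with no lead-problem leavers, because the other 5% of censored leads are counted as events too. The pooled extreme therefore does not isolate the effect of this group.

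**The case against.** The strongest reply is that the plan already sees the problem. All three primary safety sections decline to assume non-informative censoring, and the planned tipping-point range includes the case where every lead-problem leaver had an event. A reader might infer that the protocol overlooks informative censoring, but it does not. What remains is that the tipping-point analysis has no stated decision rule and does not use the withdrawal reason that 9.2 already requires.

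A reader might also infer that these leads are scored as complication-free. They are not. A censored lead leaves the risk set, and a complication before withdrawal counts as an event because earlier data are kept. The gap is limited to problems that become complications after withdrawal and within the 6-month, 3-month or 3-to-24-month window.

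A third objection concerns the remedy of making every lead-problem withdrawal a primary event. Table 20 classes problems corrected by reprogramming or other non-invasive means as observations. Counting them would set an endpoint containing non-complications against goals stated for a complication-free rate, exchanging one bias for the opposite one. That objection stands, and the primary definition should stay as it is.

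**Conclusion.** The point holds in a limited form. A lead problem that becomes a complication only after the subject has withdrawn because of it is lost to the primary test, and the complication-free rate can be biased upward when such leavers carry above-average risk. The documents do not support the stronger statement that every primary safety rate is biased upward: they give neither the share of such leavers nor their risk, and the bias vanishes at average risk.

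The 0.4 and 0.9 points for w = 1% are illustrations that rest on the assumptions listed. If every leaver would have had a complication, that is the upper case for a given w. The effect on the chance of a false pass is larger for RELIANCE 4-FRONT because its dataset is larger. One per cent of 1876 leads is about 19 leads, against a margin of about 7 events, so a modest number of withdrawals could matter. The plan's sensitivity analyses bound the effect but do not target it.

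**What to change.** 1. In Protocol 9.2, ask subjects who withdraw for a device safety or performance problem for permission to record lead status and lead-related complications through the endpoint horizon as study data. State that complications so obtained count in the primary safety endpoints, and make the bar on further data collection subject to that permission.

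2. Keep the current primary endpoint definition. In 11.1.3, 11.2.1.3 and 11.2.3, add a prespecified sensitivity analysis that counts a lead as an event at withdrawal when the reported reason is a safety or performance problem of that lead and its later outcome is unknown.

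The cost is wording in 9.2 and the analysis sections and a short addition to the consent template. Permission is already sought and the withdrawal reason is already reported. The downside is a possibly slightly less favourable complication-free rate.
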